### ***Number of patients***

There is an assumption that about 10 % of the patients will receive post remission therapy with allogeneic stem cell transplantation. Those patients will be censored in the analysis at the time point of transplantation. Further under the assumption of loss to follow-up or alternate post-remission treatment, or protocol violation in up to 25 patients, total accrual to this trial is planned for 276 patients (138 per arm).

## **7.2 Statistical Analysis Plan**

We assume an accrual time of 24 months and a follow-up time of 18 months.

The statistical analysis will be performed according to the intention to treat principle (ITT analysis). This means that every patient included into the study and randomized to one treatment arm will be evaluated in that arm, even if he does not receive study-medication, or if any other violations of the study protocol occur.

- The primary endpoint (median EFS) will be compared between both treatment arms using two-sided stratified log-rank test as described in detail. This part of the analysis is considered as confirmatory.
- Analyses of secondary endpoints will include morphologic CR-rate, overall survival, leukemia free interval and leukemia free survival.
- In an exploratory approach EFS and OS will be analyzed using stratified Cox-regression. Treatment arm and cytogenetic findings will be included as independent variables. The results of these analyses will be considered as exploratory. No  $\alpha$ -adjustment will be performed.
- In addition to the ITT-analysis a per protocol analysis (PP-analysis) will be performed. This analysis will include only those patients who could be treated with full adherence to the protocol. Besides this, the PP-analysis will parallel the ITT-analysis.

### **7.2.1 Response criteria and outcome measures**

Response criteria are defined according to the Revised Recommendations of the International Working Group for Diagnosis, Standardization of Response Criteria, Treatment Outcomes, and Reporting Standards for Therapeutic Trials in Acute Myeloid Leukemia.

### ***Efficacy***

Evaluation of bone marrow aspirate, peripheral blood counts and differentials are used to assess the efficacy of the study medication.

### ***Responding Patients:***

#### Early treatment assessment:

- 16 days after therapy
- blast reduction

#### Morphologic Complete Response (CR):

- Platelet count >100.000/μl
- Granulocyte count of >1.000/μl
- Bone marrow (aspirate with marrow spicules): < 5% blasts, Absence of Auer rods
- No evidence of persisting leukemia by flow cytometry (Sensitivity: 5%)
- Absence of extramedullary leukemia
- Transfusion independent stable hemoglobin value

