### 4.3.3 Consolidation therapy

#### 4.3.3.1 Consolidation therapy for LR patients as defined by cytogenetics and for IR patients without an HLA-identical sibling

All patients in CR/ CRi after induction therapy should receive three courses of HD-AraC consolidation therapy not earlier than one week after attaining CR/ CRi. If, in the opinion of the treating physician, the patient's condition does not allow for consolidation therapy, consolidation therapy can be postponed for up to 4 weeks after a CR/ CRi is reached. However, if the patient is not attaining CR/ CRi 5 weeks after the beginning of the second induction therapy course he/she should be classified as treatment failure (definition of event and EFS see chapter 7) and study treatment should be terminated .

Criteria for the beginning of each consolidation course: platelets > 70.000/μl and neutrophils > 1.000/μl.

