#### Complete Remission with incomplete regeneration of peripheral blood (CRi)

- Bone marrow (aspirate with marrow spicules): < 5% blasts, Absence of Auer rods
- No evidence of persisting leukemia by flow cytometry (sensitivity: 5%)
- Absence of extramedullary leukemia
- Peripheral blood with no blast cells and either less than 1.000/μl granulocytes and/or less than 100.000/μl platelets

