***Definition of Study Endpoints***

Complete remission rate (CR rate):

Proportion of patients in complete remission (CR, as defined above) after induction chemotherapy.

Event free survival (EFS):

Time interval from day 1 of study treatment until

- treatment failure (no CR/ CRi 5 weeks after the beginning of the second induction therapy course),
- relapse from CR
- relapse from morphologic leukemia-free state (CRi)
- death from any cause

whichever occurs first. The time point at which the patient is resistant to therapy or survives induction without a CR or Morphologic leukemia-free state will be noted. For a patient with none of these events before the end of study follow-up, observation of EFS will be censored at the date of his or her last follow-up examination.

Overall survival (OS):

Time interval from day 1 of study treatment to the day of death. For a patient who is not known to have died by the end of follow-up, observation of OS will be censored on the date the patient was last known to be alive.

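### CR and CRi together do not cover every leukemia-free patient: one with recovered counts who is still transfused meets neither, and the EFS rule can then score a treatment failure

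*Protocol*

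**What the plan says.** All of the definitions are in protocol section 7.2.1, with one rule repeated in section 4.3.3.1.

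- **CR** needs "Platelet count >100.000/μl", "Granulocyte count of >1.000/μl" and "Transfusion independent stable hemoglobin value", together with marrow, flow-cytometry and extramedullary criteria.
- **CRi** has the same marrow, flow-cytometry and extramedullary criteria. Its blood criterion is "Peripheral blood with no blast cells and either less than 1.000/μl granulocytes and/or less than 100.000/μl platelets". Hemoglobin is not mentioned.
- **Cytogenetic and molecular CR** repeat the full CR list, including hemoglobin, and add to it.
- **EFS** counts as an event "treatment failure (no CR/ CRi 5 weeks after the beginning of the second induction therapy course", alongside relapse and death. The EFS text treats morphologic leukemia-free state as another name for CRi.
- **The treatment failure list** contains partial remission (5–25% blasts), resistant disease (persistent AML), death in aplasia, indeterminate cause and morphologic relapse.
- **Section 4.3.3.1** uses the same five-week limit: "he/she should be classified as treatment failure". It ties the end of study treatment to that classification.

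**The concern.** CRi should hold the patients who are free of leukemia but whose blood has not fully recovered. CR has three blood criteria, and CRi opens for only two of them. A patient who misses CR on hemoglobin alone has no category.

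Two things follow. First, a patient in morphologic remission can become an early event in the confirmatory primary analysis. Second, the classification is not monotone. With granulocytes of 2,000/μl and continuing transfusion, platelets of 90,000/μl give CRi and no event, while platelets of 150,000/μl give neither category. The patient with the better count is the one scored as a failure.

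**Working it through.** **1. Enumerate the blood states.** Take a patient who meets every marrow, flow-cytometry and extramedullary criterion and has no blood blasts. Platelets may be below, equal to or above 100,000/μl; granulocytes below, equal to or above 1,000/μl; the patient is transfusion independent or dependent. That gives 3 × 3 × 2 = 18 states.

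| Class as written | States | Which |
|---|---|---|
| CR | 1 | both counts above limit, transfusion independent |
| CRi | 10 | at least one count below limit, either transfusion status |
| Neither | 7 | both above and transfusion dependent (1); at least one count exactly at its limit and none below, either transfusion status (6) |

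The total is 1 + 10 + 7 = 18.

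**2. Look for another category.** Cytogenetic and molecular CR require CR first. Morphologic leukemia-free state is only equated with CRi. In the failure list, under 5% blasts is not partial remission, there is no persistent AML, the patient is alive and has not relapsed, and a patient past second induction has completed the first course. So the EFS rule scores a failure that the failure list does not contain.

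**3. Check the timing.** In the schedule of section 5.2 (Table 14), the only marrow scheduled between day 16 of first induction and consolidation is the remission control, at the latest 35 days after second induction begins. That limit coincides with the five-week failure limit. If both counts have recovered by that marrow, no earlier scheduled marrow after second induction could have established CRi.

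**4. Reproduce the plan's figures (section 7.1).** The medians are 9 and 13.5 months, so the hazard ratio is 9/13.5 = 0.667. With two-sided α = 0.05 and 80% power:

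events = 4(1.960 + 0.842)² / (ln 1.5)² = 191, as stated.

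The event probability per arm, with λ = ln 2/median, η = 0.0074 (taken as per month), s = λ + η, A = 24 and F = 18, is

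P = (λ/s) · [1 − (e^(−sF) − e^(−s(A+F)))/(sA)].

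This gives 0.827 for control and 0.711 for Sorafenib, so 125 × (0.827 + 0.711) ≈ 192 events in 250 patients. The plan's 191 events and 250 patients are reproduced.

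**5. Illustrate the size.** The protocol gives no frequency for the gap, so the shares below are assumptions. The same design was simulated (6,000 trials per row, log-rank test). Affected patients were given an event at day 22 + 35 = 57, which is the earliest start of second induction plus five weeks.

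| Affected in both arms | Power |
|---|---|
| 0% | 80% |
| 1% | 79% |
| 2% | 79% |
| 5% | 76% |

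A separate simulation of 3,000 trials per scenario gave 75% power at 5%, with the estimated hazard ratio moving from 0.66 to 0.68. With no treatment effect, the rejection rate in the balanced scenarios stayed between 4.8% and 5.5%, so equal misclassification dilutes the effect without creating false positives.

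**6. Apply the rewording.** If CRi means that at least one CR blood criterion is not met, the 18 states become 1 CR and 17 CRi, with none left over. The 191 events and 250 patients do not change.

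**The case against.** The strongest reply is that the intent is plain. The name of CRi, the equation with a leukemia-free state and the absence of a fitting failure category all suggest that a leukemia-free patient was meant to count as a responder. That is a fair reading of intent, but the operative EFS wording is no CR or CRi by a fixed date, and the CRi criteria exclude this patient. The reply shows that the text contradicts itself. It does not show that the text is safe to apply.

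The second reply stands in part. A patient whose qualifying marrow was read while either count was still low has already attained CRi. The gap bites when the first qualifying marrow comes after both counts have recovered, or when status is judged at week five instead of by week five.

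Third, the simulations add the extra events on top of the planned medians. Section 7.1 does not say whether those medians already include such events. If they do, the loss of power is overstated.

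A reader might infer that the false events would fall more often on Sorafenib, because the protocol reports myelosuppression when it is combined with cytotoxic drugs. An assumed 5% on control against 10% on Sorafenib would cut power to 58–59%. The documents do not support that scenario. Sections 1.3.2 and 6.3.1.5 speak of low white cells, low platelets and febrile neutropenia, not of slow red-cell recovery, and low neutrophils or platelets move a patient into CRi. The protocol's renal-cell trial data (section 6.3.1.6) show anemia in 44% on Sorafenib and 49% on placebo, and grade 3 or 4 anemia in 2% and 4%. That is another disease without AML chemotherapy, so it settles nothing here, but it gives no ground for expecting an excess on Sorafenib.

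**Conclusion.** The defect is real on the wording of the protocol. Seven of 18 blood states in a leukemia-free patient are neither CR nor CRi, and the EFS definition can turn them into events that the failure list does not describe. The state that matters most is transfusion dependence with both counts recovered; the other six are boundary cases from strict inequalities on both sides.

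The size is unknown and may be small: about one point of power at 1–2% affected in both arms, and four to five points at 5%. These figures rest on assumed shares, exponential survival, a monthly reading of the loss hazard and failure scored at day 57. The conclusion does not depend on them. A between-arm bias is not shown. The reason to act is that a primary-endpoint rule gives a contradictory and non-monotone classification that is cheap to correct.

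**What to change.** For EFS classification, reword the last CRi criterion in section 7.2.1 along these lines: no blasts in peripheral blood, and at least one CR blood criterion not met (granulocytes ≤1,000/μl, platelets ≤100,000/μl, or hemoglobin not transfusion independent). CR and CRi then cover every leukemia-free patient. Make the CR and CRi criteria, the treatment failure list and the EFS definition agree with this.

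Section 4.3.3.1 ties the end of study treatment to the same classification and must be reconciled with it. No clinical rule is proposed here.

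The change needs no new test, visit or patient and leaves the sample size as it is. The cost is slightly more CRi and slightly fewer early EFS events.

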#### Complete Remission with incomplete regeneration of peripheral blood (CRi)

- Bone marrow (aspirate with marrow spicules): < 5% blasts, Absence of Auer rods
- No evidence of persisting leukemia by flow cytometry (sensitivity: 5%)
- Absence of extramedullary leukemia
- Peripheral blood with no blast cells and either less than 1.000/μl granulocytes and/or less than 100.000/μl platelets

#### Cytogenetic Complete Response (CRc):

- Platelet count >100.000/μl
- Granulocyte count of >1.000/μl
- Bone marrow (aspirate with marrow spicules): < 5% blasts, Absence of Auer rods
- No evidence of persisting leukemia by flow cytometry (Sensitivity: 5%)
- Absence of extramedullary leukemia
- Transfusion independent stable hemoglobin value
- Normal cytogenetics (based on conventional banded studies and FISH)

#### Molecular Complete Response (CRm):

- Platelet count >100.000/μl
- Granulocyte count of >1.000/μl
- Bone marrow (aspirate with marrow spicules): <5% blasts, Absence of Auer rods
- No evidence of persisting leukemia by flow cytometry (sensitivity: 5%)
- Absence of extramedullary leukemia
- Transfusion independent stable hemoglobin value
- Normal cytogenetics (based on conventional banded studies and FISH)

- Molecularly negative (no detection of pretreatment genetic markers with a methodology providing a sensitivity of at least 1:10^3)

***Treatment failure:***

Partial Remission (PR):

- Platelet count >100.000/μl
- Granulocyte count of >1.000/μl
- Bone marrow (aspirate with marrow spicules): Decrease of at least 50% in the percentage of blasts to 5% - 25%

Resistant disease:

- Patient survives ≥ 7 days post Chemotherapy (CT); persistent AML in blood or bone marrow

Death in Aplasia:

- Patient survives ≥ 7 days post Chemotherapy (CT); death while cytopenic, with aplastic bone marrow

Indeterminate cause:

- Patients who die < 7 days post CT; Patients who die > 7 days post CT with no PB blasts, but no bone marrow examination; Patients who do not complete the first course of therapy

Morphologic relapse:

- Reappearance of blasts post CT in PB or bone marrow

***Definition of Study Endpoints***

Complete remission rate (CR rate):

Proportion of patients in complete remission (CR, as defined above) after induction chemotherapy.

Event free survival (EFS):

Time interval from day 1 of study treatment until

- treatment failure (no CR/ CRi 5 weeks after the beginning of the second induction therapy course),
- relapse from CR
- relapse from morphologic leukemia-free state (CRi)
- death from any cause

whichever occurs first. The time point at which the patient is resistant to therapy or survives induction without a CR or Morphologic leukemia-free state will be noted. For a patient with none of these events before the end of study follow-up, observation of EFS will be censored at the date of his or her last follow-up examination.

Overall survival (OS):

Time interval from day 1 of study treatment to the day of death. For a patient who is not known to have died by the end of follow-up, observation of OS will be censored on the date the patient was last known to be alive.

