## 4.3.2 Induction therapy

### 4.3.2.1 Arm P (Standard cytotoxic therapy plus Placebo)

AraC	100 mg/ m  / day	continuous infusion over 24 hours	days 1-7
Daunorubicin	60 mg/ m  / day	infusion over 2 hours	days 3, 4 and 5
Placebo		2 tablets twice a day	from day 10 continuously until day 19

Table 8: Standard induction therapy plus Placebo

Patients will receive an identical second course of induction therapy starting earliest day 22 if the blast count in the bone marrow at day 16 is reduced. If there is no reduction in the blast count at day 16 or if there is even evidence of increased blast counts the patient should receive an alternative second induction therapy based on a high dose AraC application (HAM).

Alternative induction therapy - HAM (in the case of insufficient response to induction therapy I)

AraC	3g/ m  / 12hrs	infusion of 3 g/m  over 3 hours BID every 12 hours	days 1, 2 and 3
Mitoxantrone	10 mg/ m  / day	60 minutes infusion	days 3, 4 and 5
Placebo	2 tablets	twice daily	from day 10 continuously until day 19

Table 9: Alternative induction therapy plus Placebo

It is allowed to postpone the second course if the patient has an uncontrolled infection or transitory contraindications against chemotherapy. The second course can be started once these problems have been resolved.

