## 7 STUDY OUTCOME AND STATISTICAL ANALYSIS

### 7.1 Power and Sample Size Calculation, Interim Analysis

Power calculations are based on the following assumptions:

Control group:	median event free survival (EFS) 9 months
Sorafenib group:	median event free survival (EFS) 13.5 months (improvement of 50%)
Error of first kind:	$\alpha = 0.05$ (two sided)
Power:	80%
Accrual time:	24 months
Follow up:	18 months
Randomization:	1/1 allocation

To detect an improvement of median EFS from 9 months to at least 13.5 months, we need 125 evaluable patients per group i.e. a total of 250 patients to yield the necessary number of approximately 191 events.

Although all efforts will be taken to avoid patient loss to follow up, there might be a rate of loss due to various possible reasons. Censoring by transplantation in first remission will lead to an additional loss. The rate of allogeneic transplantation is assumed with about 10% of the patients. Patients receiving allogeneic stem cell transplantation will be censored for analysis at the time point of transplant. In order to account for this, exponential hazard of 0.0074 is incorporated in the sample size calculation.

Within 24 months the participating centers are able to recruit up to 300 patients fulfilling the inclusion and exclusion criteria. Taking into account a drop out rate of about 10 % the study-centers will recruit the necessary number of patients (n=276) within 24 months.

All calculations are done using SAS-Software (PROC POWER) licensed to the University of Münster.

One interim analysis and the final analysis are planned for the intent-to-treat EFS endpoint such that the overall type I error is controlled at a two-sided 0.05 level. Interim analysis will be done according to the O'Brien/Flemming approach. When 50% of the expected intent-to-treat EFS events (191 events  $\times$  0.5 = 95) are attained the first interim analysis on the intent-to-treat EFS endpoint will be conducted.

The (unblinded) interim analysis will be performed by the Studienzentrale SAL in cooperation with Institut für Medizinische Informatik und Biometrie, Münster.

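### The EFS date of an induction failure depends on when the second course starts, which leaves the log-rank test open to a modest shift towards sorafenib if that course is delayed more often in the sorafenib arm

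*Protocol*

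**What the plan says.** Section 7.2.1 (Definition of Study Endpoints) defines EFS as the "Time interval from day 1 of study treatment until" the first of several events. One of them is "treatment failure (no CR/ CRi 5 weeks after the beginning of the second induction therapy course". Section 4.3.3.1 and the remission control in Table 14 (section 5.2) use the same anchor.

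Sections 4.3.2.1 and 4.3.2.2 let the second course begin on day 22 at the earliest. They add: "It is allowed to postpone the second course if the patient has an uncontrolled infection or transitory contraindications against chemotherapy". Neither section gives a latest start. By contrast, section 4.3.3.1 limits postponement of consolidation to 4 weeks. In the first course, sorafenib or placebo is taken from day 10 to day 19.

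Two other passages bear on the point:

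- Section 3.4 requires withdrawal when study drug has been interrupted for more than 28 consecutive days. It does not say whether the planned gap between courses counts.
- After the list of EFS events, section 7.2.1 says: "The time point at which the patient is resistant to therapy or survives induction without a CR or Morphologic leukemia-free state will be noted". It does not say whether this noted time point is the EFS event date.

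**The concern.** The confirmatory analysis is a stratified log-rank test on EFS (section 7.2). For a patient who never reaches CR or CRi, the natural reading makes the event time the start of the second course plus 35 days. That start is decided after randomisation and after ten days of study drug, and infection is one of the accepted grounds for putting it off.

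The protocol itself names added treatment-related toxicity as the risk of the trial (section 2.2). It also reports myelosuppression and febrile neutropenia when sorafenib is combined with cytotoxic drugs (sections 1.3.2 and 6.3.1.5). A longer delay on sorafenib is therefore plausible, and nothing in the design forces delays to be equal. Blinding does not prevent a delay caused by toxicity.

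Induction failures fall close together in time and the log-rank test works on order. A small shift in one arm can place much of its cluster behind the other arm's cluster, so later failure would be credited as longer EFS when just as many patients had failed.

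A related gap is that the list of treatment failures in section 7.2.1 includes patients who do not complete the first course. The 5-week rule gives no date to a patient who never starts a second one.

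**Working it through.** **The plan's own figure.** The inputs are "median event free survival (EFS) 9 months" in the control arm, 13.5 months on sorafenib, two-sided 0.05, 80% power and "1/1 allocation" (section 7.1). Schoenfeld events = 4(1.960 + 0.842)² / (ln 1.5)² = 191, as stated. With exponential EFS, 24 months' accrual, 18 months' follow-up and a loss hazard of 0.0074 (taken as per month), the mean event probability is 0.769. Then 191 / 0.769 = 248, which agrees with the planned 250.

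**How the date moves.** Without postponement, failure falls on day 22 + 35 = day 57. A 7-day delay gives day 64 and a 14-day delay gives day 71. If the 28-day rule does count planned gaps, the unpostponed gap runs from day 20 to day 30 (day 10 of the second course is day 31). That is 11 days, which leaves 28 − 11 = 17 days of postponement, so both delays fit.

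**Share of patients affected.** Section 1.1 gives CR rates of 70–80%, so 20–30% do not reach CR. This is an upper bound for the share dated by the floating anchor, because CRi counts as response and early deaths are dated at death. Section 2.2 puts treatment-related mortality at up to 10% over all treatment. Shares of 15–20% are therefore also shown, as an assumption.

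**Hand calculation.** Assume no drug effect and n = 125 per arm, with k failures per arm. All placebo failures fall on one day and all sorafenib failures on a later day, with no other events in between. Observed minus expected sorafenib events are −k/2 on the first day and +k(n − k)/(2n − k) on the second. The net is

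U = −k² / [2(2n − k)].

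With total variance V about 191/4 = 47.75, the z shift is U/6.91, the apparent hazard ratio is exp(U/V), and the one-sided error is Φ(−1.96 + |z|).

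| Failure share | k | U | z shift | Hazard ratio | One-sided error |
|---|---|---|---|---|---|
| 15% | 18.75 | −0.76 | −0.11 | 0.98 | 3.2% |
| 20% | 25 | −1.39 | −0.20 | 0.97 | 3.9% |
| 25% | 31.25 | −2.23 | −0.32 | 0.95 | 5.1% |
| 30% | 37.5 | −3.31 | −0.48 | 0.93 | 6.9% |

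Simulation of a 7-day delay with no spread in start days gives 4.1% at 20% and 7.0% at 30%, in line with the table. U grows roughly with the square of the failure share, so the result depends heavily on that share.

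**Simulation with spread in start days.** There is no drug effect and overall median EFS is 9 months. Each setting has 250 or 276 patients and 4,000 to 8,000 trials, with an unstratified log-rank test. Second-course starts vary by about one week to ten days (assumption). Ranges are across runs with slightly different settings. Monte Carlo error is about 0.2 to 0.4 points.

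| One-sided error favouring sorafenib | 15% fail | 20% | 25% | 30% |
|---|---|---|---|---|
| 7 days, every sorafenib patient | 2.8% | 3.4–3.6% | 4.0–4.1% | 4.9–6.2% |
| 14 days, every sorafenib patient | 3.7% | 4.0–4.5% | 5.4–5.5% | 7.8–8.0% |
| 14 days, 30% of sorafenib patients | 2.6% | 2.8–3.1% | not run | 3.4–3.9% |
| Common failure date | not run | 2.6–3.1% | 2.3% | 2.9% |

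Apparent hazard ratios for 7 and 14 days in every sorafenib patient are 0.97 and 0.97 at a 20% share, and 0.95 and 0.93 at 30%. Median EFS stays at about 9 months in both arms throughout.

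**The case against.** A reader might infer that any drug-related delay would pass for an EFS benefit. The documents and the figures do not support that.

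- Postponement is allowed only on stated grounds, so it would apply to some patients and not to all. A 14-day delay in 30% of sorafenib patients is close to invisible.
- Even with every sorafenib patient delayed by 14 days, the hazard ratio is 0.93 or nearer to 1, against a design value of 9/13.5 = 0.667.
- The stated error is two-sided. At a 20% share and 7 days the tails are 3.5% + 1.5% = 5.0%, so the total is unchanged. At 30% and 14 days the total does rise, to 8.5%.
- The objective is worded in terms of median EFS, which does not move.

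These limits on size stand. They do not remove the point, because the confirmatory test is the log-rank test and a shift towards sorafenib is the error that matters.

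A reader might also infer that postponement has no limit. That holds for the text of sections 4.3.2.1 and 4.3.2.2, but the 28-day rule in section 3.4 may cap it indirectly. The cap is uncertain, and withdrawn patients stay in the intention-to-treat analysis.

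Finally, the event date might be the noted time point of resistance, which Table 14 allows to be earlier than 35 days, and a statistical analysis plan could settle this. That is fair. But the protocol then offers two candidate dates without choosing, and a date of documented resistance after the second course would still move with that course.

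**Conclusion.** The defect is real and modest. As written, the primary endpoint ties the event time of induction failures to a start date that study drug could influence and for which no latest day is stated.

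The delay is an assumption, because the documents report none for either arm. The false-positive figures are about 3–5% one-sided at a 15–20% failure share and about 4–8% at 25–30%, for 7 to 14 days in every sorafenib patient. They fall to about 2–4% if 30% of sorafenib patients are delayed by 14 days. The 25–30% figures are an upper bound, because they count CRi patients and early deaths as dated failures. The simulations also use an unstratified test and ignore the interim look.

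A reader might conclude that EFS and OS must instead be counted from randomisation. The point does not require it: a common failure date counted from day 1 removes the dependence and leaves the time origin alone.

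**What to change.** In the EFS definition in section 7.2.1:

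- Keep the 5-week rule for deciding who has failed induction.
- Give every induction failure in both arms one common event time that does not depend on when the second course began, for example one fixed study day counted from day 1 and chosen on statistical grounds. This also dates failures who never start a second course.
- State what the noted time point of resistance is used for.
- Report the analysis with actual failure dates as a sensitivity analysis.

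The cost is endpoint wording and one extra analysis. Failure times become conventional and no longer observed, and they are re-ordered slightly against deaths near the chosen day, so the text should say which date applies when a patient dies around it. The 191 events and the sample size stay as they are, and no clinical rule on postponement is altered.
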